4.1 Full Inclusion Criteria

A subject must meet all of the following criteria to be eligible to participate in this study:

1. Provides written informed consent prior to initiation of any study procedures.
2. Agrees to comply with planned study procedures and be available for all study visits.
3. Agrees to the collection of venous blood per protocol.
4. Male or non-pregnant female, 18 to 45 years of age, inclusive, at time of enrollment.
5. Body Mass Index 18-35 kg/m², inclusive, at screening.
6. Woman of childbearing potential must have a negative urine pregnancy test within 7 days prior to study initiation.
7. Oral temperature is less than 100.0°F (37.8°C).
8. Pulse no greater than 90 beats per minute.
9. Systolic BP is 85 to 150 mmHg and Diastolic BP ≤ 90 mmHg, inclusive.
10. Clinical screening laboratory evaluations are within acceptable normal reference ranges at the clinical laboratory being used.

4.2 Full Exclusion Criteria

A subject who meets any of the following criteria will be excluded from participation in this study:

1. Positive urine pregnancy test at screening.
2. Has any medical disease or condition that, in the opinion of the site PI or appropriate sub-investigator, precludes study participation.¹
3. Plans to travel away from the study site area during the term of study to a location or in a manner that may interfere with full completion of the study per protocol.
4. Presence of self-reported or medically documented significant medical or psychiatric condition(s).²
5. Has an acute illness³, as determined by the site PI or appropriate sub-investigator, with or without fever [oral temperature $>37.8^{\circ}\text{C}$ (100.0°F)] within 72 hours of study day 1.
6. Reports a recent positive test result for hepatitis B surface antigen, hepatitis C virus antibody, or HIV-1 antibodies at screening.
7. Currently enrolled in or plans to participate in another clinical trial with an interventional investigational agent that will be received during the study period.⁵
8. Has a history of hypersensitivity or severe allergic reaction (e.g., anaphylaxis, generalized urticaria, angioedema, other significant reaction) to nitrates, nitrites or sun exposure.
9. Active use of any medications that may be associated oral pharyngeal or mucosal irritation.
10. Has any blood dyscrasias or significant disorder of coagulation.
11. Has a history of alcohol abuse or other recreational drug (excluding cannabis) use within 1 month of Study Day 1.
12. Has any oral abnormality that would interfere with device use, or intra-oral metal body piercings that cannot be removed for the duration of the study. Metal orthodontia is permitted as braces will be covered by the device mouthpiece.
13. Receipt of any other SARS-CoV-2 or COVID19 experimental coronavirus investigational product within 30 days of screening.

¹*Including medical diseases or conditions that would place the subject at an unacceptable risk of injury, render the subject unable to meet the requirements of the protocol or may interfere with the evaluation of responses or the subject's successful completion of this trial.*

²*Significant medical or psychiatric conditions include but are not limited to: respiratory disease (e.g., chronic obstructive pulmonary disease [COPD], asthma) requiring current daily medication.*

Significant cardiovascular disease (e.g., congestive heart failure, cardiomyopathy, ischemic heart disease).

Neurological or neurodevelopmental conditions (e.g., epilepsy, stroke, seizures in the last 3 months, encephalopathy, focal neurologic deficits, Guillain-Barré syndrome, encephalomyelitis or transverse myelitis).

Ongoing malignancy or malignancy in remission within the last six months excluding basal cell and squamous cell carcinoma of the skin, which are allowed.

An autoimmune disease without a defined non-autoimmune cause.

Any active immunodeficiency of any cause.

³*An acute illness which is nearly resolved with only minor residual symptoms remaining is allowable if, in the opinion of the site PI or appropriate sub-investigator, the residual symptoms will not interfere with the ability to assess safety parameters as required by the protocol.*

⁴*study drug, biologic or device.*

⁵*Including licensed or unlicensed vaccine, drug, biologic, device, blood product, or medication.*

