1.1.3 Inclusion Criteria (abbreviated)

See full inclusion criteria in Section 4.1

A subject must meet all the following criteria to be eligible to participate in this study:

1. Provides written informed consent prior to initiation of any study procedures.
2. Be able to understand and agrees to comply with planned study procedures and be available for all study visits.
3. Agrees to the collection of venous blood per protocol.
4. Male or non-pregnant female, 18 to 45 years of age, inclusive, at time of enrollment.
5. Body Mass Index 18-35 kg/m², inclusive, at screening.
6. No active disease process (chronic or acute) or physical or mental conditions or attributes at the time of screening, which in the opinion of the PI, will prevent full use and assessment of RD19.
7. Oral temperature is less than 100.0°F (37.8°C).
8. Pulse no greater than 90 beats per minute.
9. Systolic blood pressure (BP) is 85 to 150 mmHg, Diastolic blood pressure (BP) is ≤ 90, inclusive.
10. Clinical screening laboratory evaluations are within acceptable normal reference ranges at the clinical laboratory being used in the study

Exclusion Criteria (abbreviated)

See full exclusion criteria in Section 4.2

A subject who meets any of the following criteria will be excluded from participation in this study:

1. Positive urine pregnancy test at screening.
2. Has any medical disease or condition that, in the opinion of the site Principal Investigator (PI) or appropriate sub-investigator, precludes study participation.
3. Presence of self-reported or medically documented significant medical or psychiatric condition(s).
4. Has an acute illness, as determined by the site PI or appropriate sub-investigator, with or without fever [oral temperature >37.8°C (100.0°F)] within 72 hours prior to screening.
5. Has participated in another investigational study involving any SARS-CoV-2/COVID-19 interventional investigational product within 30 days of screening.
6. Has a history of hypersensitivity or severe allergic reaction (e.g., anaphylaxis, generalized urticaria, angioedema, other significant reaction) to nitrates, nitrates or sun exposure.

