3. STUDY DESIGN

3.1 Overall Design

This first-in-man (FIM) phase I study will evaluate the acute safety, tolerability, and device acceptability for use among 25 healthy volunteers between the age of 18 and 45. Based on the results of numerous preclinical studies, a single dose (9 joules/cm²) and schedule (twice a day, separated by at least 4 hours, preferably 8 to 12 hours apart) will be evaluated.

Safety and tolerability (local reactogenicity) will be assessed actively at the following study days: screening (baseline set), 1, 7 and 14, and on non-clinic visit days by collection of these data by history during clinic visits via a memory aid (diary cards). Volunteers will be encouraged to promptly contact designated clinical trial staff or the one of the Sponsor's Emergency Response Team for AEs of a medically urgent nature.

A Comprehensive Metabolic Panel, as well as CBC with differential, urinalysis, and pregnancy testing will be performed at screening and at Day 14 or early termination (and potentially during unscheduled) clinic visits. Hematological safety assessments (evaluation of methemoglobinemia) will be performed at all visits.

Study volunteers will be asked to immediately contact the clinical coordinator and/or the PI in all instances where they experience an AE of greater than moderate intensity. Volunteers will be instructed to report to the clinical trial unit for an unscheduled visit or to seek the appropriate level of medical care based on the nature of their AE/SAE. In all such instances, all relevant information pertaining to these significant medical events will be captured on the appropriate e-CRFs.

Hematology safety laboratory evaluations will be performed at screening, as well during all scheduled clinic visits. Laboratory assessments may be part of the evaluation of medically attended AE evaluation and for all SAEs.

Upon ratification of the CTA, the site will begin pre-recruitment outreach efforts of potential volunteers within M3-WRA's database to ascertain "interest in general" in this study. Official recruitment which may include fliers, letters, telephone calls, etc. and specific recruitment of potential subjects who have previously participated in other clinical studies conducted at the site will occur only after formal IRB approval. Other forms and/or mechanisms of recruitment may also be used. The IRB will approve the recruitment process and all materials prior to use.

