6. STUDY ASSESSMENTS AND PROCEDURES

6.1 Screening Assessments

6.1.1 Screening Procedures

There is a small amount of risk to subjects who report that they are in good health but have an unknown health problem at the time of screening. At the screening visit, and prior to any other study-related activities, the participating clinical site PI or appropriate sub-investigator will provide the subject with detailed study information and will obtain written informed consent.

Some or all of the following assessments are performed during the screening visit to determine eligibility requirements as specified in the inclusion and exclusion criteria:

- Obtain medical history focusing on conditions per protocol exclusion criteria.
- Review pre-study medications and therapies up to 10 days prior to the start of screening that could impact the use of, or response to, the device and record on the appropriate e-CRF.
- Measure vital signs (HR, BP, and oral temperature) and height and weight for determination of BMI.
- Perform full physical examination which will include assessments of the following organs and organ systems: skin, head, ears, eyes, nose, and throat (HEENT), neck, lungs, heart, liver, spleen, abdomen, extremities, lymph nodes (axillary and cervical), and nervous system.
- Obtain blood and urine for clinical screening laboratory evaluations:
 - Hematology
 - CBC with differential
 - Methemoglobin level (Pulse Ox method)
 - CMP (fasting or non-fasting)
 - Urine pregnancy test (in women of childbearing potential)
- Review inclusion and exclusion criteria.

Clinical screening laboratory evaluations will be performed locally by the site laboratory.

The overall eligibility of the subject to participate in the study will be assessed once all screening values are available. The screening process can be suspended prior to complete assessment at any time if exclusions are identified by the study team.

Study subjects who qualify for inclusion will be scheduled for enrollment and their day 1 visit.

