7.2 Sample Size Determination

SAMPLE SIZE CONSIDERATION - OPEN LABEL

This study is designed as an open-label study, without a placebo arm. Given the small sample size, the use of a placebo group is unlikely to improve understanding of AEs. Additionally, having the study unblinded will facilitate the need for rapid review and dissemination of study data for public health reasons.

Rare AEs are not demonstrable in a clinical study of this size; however, the probabilities of observing one or more AEs given various true event rates are presented in the table below. With the assumption that all enrolled subjects will likely complete the trial and safety visits in this relatively short duration study, the following statistical considerations apply. With 25 subjects, the chance of observing at least one AE of probability 20% or more is approximately 97%. Therefore, if no AEs of a given type occur in the study, we can be 97% confident that they will occur in fewer than 20% of people once RD19 is implemented. Also with 25 subjects, the chance of observing at least one AE of probability 5% or more is 90%. Therefore, if no AEs of a given type occur in the study, we can be 90% confident that such adverse event will occur in fewer than 5% of people once RD19 is implemented.

| N | “True” Event Rate | Probability of Observation (%) |
|---|-------------------|--------------------------------|
| 2 | 0.1% | 2.5 |
| | 0.5% | 12.0 |
| | 1.0% | 23.4 |
| | 2.0% | 43.4 |
| | 3.0% | 61.3 |
| | 4.0% | 74.8 |
| | 5.0% | 90.3 |
| | 10.0% | 92.4 |
| | 15.0% | 94.3 |
| | 20.0% | 97.5 |

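### The 30-day look-back for investigational products covers only SARS-CoV-2/COVID-19 products, so a volunteer who has just finished a non-COVID agent can enter this uncontrolled arm of 25

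*Combined protocol and SAP*

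**What the plan says.** Three eligibility rules bear on other investigational products.

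- Section 4.2, exclusion 13: "Receipt of any other SARS-CoV-2 or COVID19 experimental coronavirus investigational product within 30 days of screening".
- Section 1.1.3, abbreviated exclusion 5: "Has participated in another investigational study involving any SARS-CoV-2/COVID-19 interventional investigational product within 30 days of screening".
- Section 4.2, exclusion 7: "Currently enrolled in or plans to participate in another clinical trial with an interventional investigational agent that will be received during the study period". Its footnote 5 makes the product scope wide: "Including licensed or unlicensed vaccine, drug, biologic, device, blood product, or medication".

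On recruitment, Section 3.1 provides for "specific recruitment of potential subjects who have previously participated in other clinical studies conducted at the site". At screening, Section 6.1.1 asks staff to "Review pre-study medications and therapies up to 10 days prior to the start of screening", limited to products that could bear on use of, or response to, the device. That step makes a record; it is not itself an exclusion.

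On design, Section 7.2 states: "This study is designed as an open-label study, without a placebo arm".

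**The concern.** Exclusion 13 ties the look-back to the indication of the earlier product, but carry-over does not depend on indication. Exclusion 7 has the wide product scope that exclusion 13 lacks, but its timing is set by dosing during this study. Between the two lies a gap: any non-COVID drug, biologic, vaccine or device whose dosing ended shortly before screening.

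The primary endpoint is the frequency, grade and attribution of AEs in a single open-label group. Several solicited events (headache, nausea, fever, chills) are non-specific. Without a concurrent comparison, a late or worsening effect of another experimental agent looks the same in the frequency tables as an effect of the device.

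**Working it through.** **Step 1. Is there a gap?** Take a volunteer whose last dose of a non-COVID investigational agent came shortly before screening, and test each rule that might apply.

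| Rule | Looks back? | Covers a non-COVID agent? | Excludes this volunteer? |
|---|---|---|---|
| Exclusion 13 | Yes, 30 days | No | No |
| Synopsis exclusion 5 | Yes, 30 days | No | No |
| Exclusion 7 | No; turns on receipt during this study | Yes (footnote 5) | No, once that trial is over |
| Exclusion 2 | Not a look-back rule; concerns a disease or condition | Not addressed | No |
| Exclusion 9 | Active use only, of medicines linked to oral or mucosal irritation | Only if of that kind and still in use | No |

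Exclusion 2 reads "Has any medical disease or condition that, in the opinion of the site PI or appropriate sub-investigator, precludes study participation"; having received an investigational agent is not in itself a disease or condition.

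Exclusion 7 can be read in two ways. If the clause on receipt during the study governs both current and planned enrolment, a volunteer in another trial's follow-up with dosing finished is eligible. If it governs only planned enrolment, that volunteer is excluded, but one who has completed the other trial is still eligible. The gap survives both readings; only its width changes.

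**Step 2. Where would a carry-over effect be counted?**

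- Section 6.2.1 records AEs in the reporting period whatever their cause, and Section 6.1.2 makes every abnormal finding after device use an AE.
- Section 7.4.1 summarises solicited AEs by severity and as any versus none, with no split by relationship. A carry-over headache counts in full.
- Section 7.4.1 cross-tabulates non-serious unsolicited AEs by relationship. There the event still counts in the overall rate, but can be shown as Not Related.
- Section 6.2.9 lets close timing to device use support a rating of Related. It allows Not Related when another cause is established, which is harder if the earlier agent was never recorded.

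**Step 3. Size.** Inputs: n = 25 (Section 4) and exact confidence intervals (Section 7.4.1). The plan gives no figure for this point, so there is none to reproduce.

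- Effect of one subject on a proportion: 1/25 = 4 percentage points, provided that subject would otherwise have had no event of that type.
- 0/25: upper exact 95% limit = 1 − 0.025^(1/25) = 13.7%.
- 1/25: Clopper-Pearson 95% CI 0.1% to 20.4%.
- 2/25 = 8%: 1.0% to 26.0%.
- 3/25 = 12%: 2.5% to 31.2%.

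The number of recent participants, and the chance that each has a new event, are not in the documents. As an assumption only: with m such subjects and a chance q of a carry-over event that would not otherwise have occurred, the expected inflation is m × q / 25. For m = 1, q = 0.1 it is 0.4 percentage points; for m = 3, q = 0.5 it is 6.0 points.

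**The case against.** The case on the other side is substantial and narrows the point.

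*Baseline rules remove much of the carry-over.* Conditions present at screening are not AEs (Section 6.2.1), screening laboratory values must be within acceptable normal ranges (Section 4.1, criterion 10), and reactogenicity is assessed just before first use (Section 6.2). This stands. Only effects that appear or worsen after first device use remain.

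*Attribution offers a way out.* A reader might infer that every effect of the other agent would be counted as caused by RD19. The documents do not support that: Section 6.2.9 provides Not Related and Null Determination. The exposure lies mainly in the solicited proportions, which ignore attribution.

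*The 10-day medication review.* A reader might infer that a COVID product taken 11 to 30 days before screening would be missed. That does not follow. Section 6.1.1 lists review of the inclusion and exclusion criteria as its own step, and Section 4 requires a clinician to confirm them, so exclusion 13 is checked directly.

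*The pausing rule.* A reader might infer that carry-over could halt the study. Section 5.5.1 requires three or more subjects with Grade 3 or higher AEs in the same SOC, considered related to RD19. Nothing in the documents makes that plausible from carry-over.

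*Likelihood.* Section 3.1 speaks of earlier participation, not recent participation, and it is one recruitment route among several. This also stands: the route makes the case realistic, but its frequency is unknown.

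*Descriptive study.* No hypothesis is tested, and in any uncontrolled study non-specific symptoms are hard to attribute. True, but the AE proportions are the main output, and this source of noise can be removed at little cost.

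**Conclusion.** The point holds as a gap in the eligibility rules. The look-back is limited to SARS-CoV-2/COVID-19 products, exclusion 7 does not supply one for other agents, and no other rule does so. Followed as written, the plan admits a volunteer who has recently completed a non-COVID investigational agent.

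The consequence is limited: 4 percentage points on an AE's rate for each subject with a new or worsening event due to the other agent who would otherwise have had none. This assumes that all 25 subjects are in the denominator; in a smaller per-protocol group each subject weighs 1/n, which is more. How many subjects this would involve cannot be derived from the documents. It is a cheap improvement to the primary safety data, not a flaw that invalidates the study.

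**What to change.** 1. Widen exclusion 13 and synopsis exclusion 5 to receipt of any investigational drug, biologic, vaccine or device within the protocol's own 30-day window, or another window that the sponsor justifies, since carry-over varies by agent.
2. Reword exclusion 7 so that, together with exclusion 13, it leaves no gap between past and future dosing. State whether the clause on receipt applies to current enrolment, planned enrolment or both. A blanket exclusion of anyone enrolled elsewhere, whenever the agent was given, is not needed; it would bar people in long-term follow-up who were dosed long ago.
3. Have the Section 6.1.1 review record prior investigational products over the same window as exclusion 13, so that a possible alternate cause is on file when events are attributed.

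The cost is wording changes in four places (exclusions 13 and 7, synopsis exclusion 5 and Section 6.1.1) and a slightly smaller pool from which to fill 25 places. No visit or test is added.

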4.3 Study Volunteer Selection, Retention & Compensation

4.3.1 Recruitment

Potential subjects will learn about the study via IRB-approved recruitment strategies, including direct mailing, recruitment from an IRB-approved trial registry and local advertisements/flyers. Screening will begin with a brief IRB-approved telephone call from study staff. Information about the study will be presented to potential subjects and questions about their health and ability to comply with the study visit schedule will be asked of potential subjects to presumptively determine eligibility. Appointments will be made at the clinical trial unit for potential subjects who are interested in the study for further screening procedures and additional protocol-specific information.

4.3.2 Retention

Study retention strategies will include education and explanation of the study schedule and procedures during screening and enrollment visits and restriction of enrollment to persons who can attend all study visits. Participating subjects will be reminded of subsequent visits during each visit, and study staff will contact subjects prior to appointments. Study staff will contact subjects who miss appointments to encourage them to return for completion of safety evaluations.

4.3.3 Compensation Plan for Subjects

Subjects will be compensated for their participation in this trial. Compensation will be in accordance with local IRB requirements, and subject to local IRB approval. Reimbursements will be disbursed at specific timepoints during the study with the total amount contingent on completing study procedures.

4.3.4 Costs

There is no cost to subjects for the research tests, procedures/evaluations or study device while taking part in this trial. Procedures and treatment for clinical care may be billed to the subject, subject's insurance or third party.

5. STUDY DEVICE

5.1 Regulatory Considerations

5.1.1 Preliminary Regulatory Pathway for EmitBio™ RD19

The Food and Drug Administration (FDA) plays a critical role in protecting the United States from threats such as emerging infectious diseases, including the COVID-19 pandemic. To date, the agency has utilized various mechanisms to expand access for drugs, grant emergency use authorization (EUA) for certain diagnostic and treatment approaches and has issued policies for medical devices without premarket notification during the COVID-19 public health emergency.

The most applicable policy document for the EmitBio™ RD19 device and its proposed indication for use is the “*General Wellness: Policy for Low Risk Devices*” issued by the Food and Drug Administration Center for Devices and Radiological Health (FDA-CDRH) on September 27, 2019.

At this time RD19 is one of multiple products under development at EmitBio™ across the respiratory infection landscape. The safety data collected will be useful in determining the final regulatory pathway for RD19 and subsequent devices.

With the above guidance and policy documents from the FDA, and the company’s assessment that RD19 is a Not Significant Risk (NSR) device (August 3, 2020), EmitBio™ will follow the guidance of 21 CFR 812 as an NSR device and seek IRB approval for this protocol as a minimal risk protocol requiring only IRB, but not FDA-CDRH, review and approval.

EmitBio™ will undertake a Phase I clinical trial, RD19-01-3Q20, under 21 CFR 812 as a Not Significant Risk (NSR), Minimal Risk protocol to assess the acute safety and local reactogenicity of RD19 commencing this month (August 2020). Results will be available in September 2020.

5.1.2 Proposed Label Claim/Indication for Use:

The EmitBio™ RD19 device uses blue light to boost the body's natural immune response, which when combined with social distancing and proper mask use as part of healthy living, may help to reduce the risk of infection by respiratory viruses like influenza and SARS-CoV-2.

5.1.3 Medical Device Quality System:

EmitBio™ will operate under an established Quality Management System, with a commitment for continuous improvement and effectiveness, in accordance with the requirements of the customers and applicable international standards. Specifically, the EmitBio™ Quality Management System is compliant with the requirements of the FDA Quality Systems Regulations (QSR).

